3. LIST OF ABBREVIATIONS

The following abbreviations are used in this study protocol.

Table 3: Abbreviations and Specialist Terms

Abbreviation	Definition
AE	adverse event
AESI	adverse event of special interest
ALT	alanine aminotransferase
ANOVA	analysis of variance
AOC	area over the curve
AST	aspartate aminotransferase
AUC	area under the concentration-time curve
AUC ₀₋₉₀	area under the concentration-time curve from 0 to 90 minutes post-dosing
AUC ₀₋₁₈₀	area under the concentration-time curve from 0 to 180 minutes post-dosing
AUC ₀₋₃₆₀	area under the concentration-time curve from 0 to 360 minutes post-dosing
BGM	blood glucose measurement
BMI	body mass index
BP	blood pressure
CLIA	Clinical Laboratory Improvement Act
C _{max}	maximum plasma concentration
CRF	case report form
CRO	contract research organization
eCRF	electronic case report form
ECG	electrocardiogram
EDC	electronic data capture
FDA	Food and Drug Administration
GCP	Good Clinical Practice
GLP	Good Laboratory Practices
GLP-1	Glucagon-like peptide-1
HbA1c	glycated hemoglobin
HBV	hepatitis B virus
HCV	hepatitis C virus
HIPAA	Health Insurance Portability and Accountability Act
HIV	human immunodeficiency virus
HR	heart rate
IB	Investigator's Brochure
I:C	insulin-to-carbohydrate
ICF	informed consent form
IEC	Independent Ethics Committee
ICH	International Conference on Harmonisation
IME	important medical event
IND	Investigational New Drug

Abbreviation	Definition
IRB	institutional review board
IUD	intra-uterine device
IWRS	Interactive Web Response System
MedDRA	Medical Dictionary for Regulatory Activities
NRS	Numeric Rating Scale
PD	pharmacodynamics
PE	physical examination
PK	pharmacokinetic
PT	Preferred Term
PRAM9	Co-formulation of a fixed-ratio combination of 9 µg pramlintide per unit of regular insulin
RBC	red blood cells
SAE	serious adverse event
SAP	Statistical Analysis Plan
SC	subcutaneous
SD	standard deviation
SOC	System Organ Class
T1D	Type 1 diabetes mellitus
TEAE	treatment-emergent adverse event
Tmax	time to maximum plasma concentration
ULN	upper limit of normal
WHO	World Health Organization

4. INTRODUCTION

4.1. Medical Need

The response of insulin and amylin to food intake is absent in patients with type 1 diabetes (T1D) due to autoimmune β -cell destruction [Ludvik 1991, Koda 1992, Herrmann 2016]. Insulin therapy is the primary treatment option for patients with T1D.

Despite considerable advances in insulin chemistry, delivery, and pharmacology, only a small percentage of diabetic patients achieve near normal glycemic levels with insulin replacement alone [Klein 1996, Whitehouse 2002]. The increased risk of severe hypoglycemia and undesired weight gain that usually accompany glycemic improvements with insulin therapy represent major obstacles toward achieving satisfactory glycemic control [DCCT 1997, DCCT 1988, Purnell 1998].

Pramlintide [AstraZeneca Pharmaceuticals, LP, 2016], a soluble, nonaggregating, equipotent synthetic analog of amylin, is approved by the FDA and used to treat T1D and T2D patients who are unable to obtain near-normoglycemia with insulin therapy. In a study conducted in subjects with T1D with a mean HbA1c of 8.1 (mean age=41 years, mean duration of diabetes=20 years, mean body mass index (BMI)=28 kg/m²), pramlintide (SYMLIN[®]) or placebo was administered at major meals as an add on to insulin therapy at a dose of 15 μ g and titrated upward at weekly intervals of 15 μ g to maintenance doses of 30 μ g or 60 μ g. The insulin dose was reduced by 30% to 50% in order to minimize the risk of developing hypoglycemia. Those who received pramlintide had a mean percent reduction of 7.1% in the mealtime insulin dose at 6 months post study drug administration initiation compared with 2.4% reduction in the placebo group [AstraZeneca Pharmaceuticals, LP, 2016].

Many clinical studies that add pramlintide to insulin have demonstrated improved control of blood sugar, lower hemoglobin A1c, and better patient satisfaction and well-being. However, the benefits of these products used together also are associated with increased risk of pramlintide-associated nausea and vomiting ; increased number of required injections; and tailoring of insulin and pramlintide doses [AstraZeneca Pharmaceuticals, LP, 2016].

Although pramlintide does not cause hypoglycemia, when combined with insulin, the risk of severe hypoglycemia is increased. In subjects with T1D, in 6-month controlled trials without insulin reduction at initiation, the incidence of severe hypoglycemia was 16.8% (0 to 3 months, n=716) in subjects receiving pramlintide and insulin, as compared with 10.8% (0 to 3 months, n=538) in subjects receiving placebo and insulin [AstraZeneca Pharmaceuticals, LP, 2016].

In addition to the risk of hypoglycemia, separated administrations of insulin and amylin at distinct times before meals, varying doses, and multiple injection sites are impediments to patient compliance that counter the known therapeutic benefits of pramlintide. A fixed-ratio, single-injection of a co-formulated insulin-pramlintide preparation would be desirable in mimicking physiological patterns [Riddle 2015, da Silva 2018].

4.2. Xeris' Pramlintide-Insulin Injection

Xeris Pharmaceuticals has developed a liquid-stable, co-formulation of a fixed-ratio combination of 9 μ g pramlintide per unit of regular insulin (PRAM9) that can be delivered as a single SC

injection. The fixed-dose combination is designed to reduce the treatment burden associated with concomitant insulin and pramlintide therapy, ie, reduce the number of daily aggregate injections because the pramlintide would not require separate mealtime injections.

In nonclinical studies, the pharmacokinetic (PK) and pharmacodynamic (PD) characteristics of pramlintide and Humulin® (or regular insulin) or Humalog® (lispro insulin) were studied in normal and streptozotocin-induced diabetic rats (STZ; mimicking T1D). Treatments were given as separate injections of commercial products or as Xeris' pramlintide-insulin combined dose single injection. Consistent with pramlintide's known pharmacological action, there was no glucose lowering with pramlintide alone for either the commercial or Xeris formulation. Additionally, glycemic profiles for pramlintide were similar to saline or Xeris vehicle administered by SC injection in rats. Xeris' pramlintide-insulin formulation showed a longer duration of glucose lowering compared to separate injections of commercial pramlintide (Symlin®) and insulin (Humulin®).

This clinical study has been designed to compare the PD, PK, and safety of PRAM9 with regular insulin and regular insulin plus pramlintide (co-administered as separate injections) when injected subcutaneously (SC) in the abdomen of fasted adults with T1D. A detailed description of, and rationale for the dosing regimen for this study is located in [Section 9.1](#).

5. STUDY OBJECTIVES AND PURPOSE

5.1. Primary Objective

The primary objective of this study is to evaluate the PD properties of a single dose of PRAM9 compared to single doses of regular insulin and regular insulin plus pramlintide (co-administered as separate injections) in adults with T1D.

5.2. Secondary Objectives

The secondary objectives of this study are to evaluate the safety and PK profiles of a single dose of PRAM9 compared to single doses of regular insulin and regular insulin plus pramlintide (co-administered as separate injections) in adults with T1D.

5.3. Study Endpoints

Primary

The PD effects upon plasma glucose levels will be compared between the treatments as defined by the following primary endpoint:

- Area under the curve area from administration to 180 min (AUC₀₋₁₈₀) (mg/dL × minutes) for plasma glucose > 180 mg/dL

Secondary

See [Section 13.3](#) for a complete listing of secondary endpoints to be analyzed in this study. Additionally, full description of secondary endpoints will be included in a separate Statistical Analysis Plan (SAP).

6. INVESTIGATIONAL PLAN

6.1. Overall Study Design

This is a randomized, open-label, active-controlled, single-dose, 3-treatment, 3-period, 3-way crossover, comparative PD and PK inpatient study in adults with T1D. The study comprises 5 visits: Screening (Visit 1), Treatment Periods (Visits 2 – 4), and Follow-Up (Visit 5).

To determine eligibility, subjects will complete the Screening procedures (Visit 1) up to 28 days before the first treatment visit (Visit 2). Subjects will be instructed to eat normally and take their usual medications, but to refrain from alcohol for 24 hours prior to checking in for treatment visits.

Treatment Periods

For Treatment Period Visits 2 through 4, eligible subjects will be instructed to arrive for an overnight stay at the clinical research facility on the day prior to each treatment visit. At the clinic, subjects will be given a standardized dinner meal, and instructed to take their prescribed evening mealtime insulin regimen and basal insulin dose. The subjects will fast after midnight but will be allowed to drink water ad libitum (ie, tap water, bottled water, distilled water, etc. [water without carbohydrates]) and take any prescribed medications.

During each Treatment Period Visit, subjects will receive a single SC dose of PRAM9, regular insulin, or co-administered regular insulin plus pramlintide. On the morning of each treatment visit and prior to dosing, a fasting blood sample will be tested using a blood glucose meter (BGM) to confirm that blood glucose is in the range of 80 to 150 mg/dL.

- If the blood glucose is > 150 mg/dL after repeat test, then the investigator may treat with an intravenous (IV) bolus dose of regular insulin, per discretion, to bring the subject into the required blood glucose range. Before initiating study treatment, at least 40 minutes should have passed from the last dose of administered insulin and the subject's glucose level should be within the range of 80 to 150 mg/dL.
- If the blood glucose is < 80 mg/dL after repeat test, then the investigator may treat with oral glucose tabs/solution or IV glucose, per discretion, to bring the subject into the required blood glucose range. Before initiating study treatment, at least 30 minutes should have passed from the last dose of administered glucose and the subject's glucose level should be within the range of 80 to 150 mg/dL.
- If the subject's blood glucose cannot be optimized to 80 to 150 mg/dL within 2 hours, then the visit should be rescheduled after a minimum 24-hour wait, per investigator's discretion.

At Visit 2, once blood glucose is confirmed to be within the range of 80 to 150 mg/dL, subjects will be randomized to their study drug treatment sequence.

Table 4: Sequence of Study Drug Administration

Cohort	Period 1	Period 2	Period 3
1	PRAM9	Regular insulin	Regular insulin + pramlintide
2	Regular insulin	Regular insulin + pramlintide	PRAM9
3	Regular insulin + pramlintide	PRAM9	Regular insulin
4	PRAM9	Regular insulin + pramlintide	Regular insulin
5	Regular insulin	PRAM9	Regular insulin + pramlintide
6	Regular insulin + pramlintide	Regular insulin	PRAM9

Insulin-to-carbohydrate calculations will be used to identify subject doses. All subjects will get flexible doses of insulin, pramlintide, and PRAM9. See [Section 9.1](#) for complete information on study drug dosing. The dose of regular insulin is calculated to correspond to a ratio of 9 µg of pramlintide for every 1 unit of insulin. Additionally, the dose of regular insulin is calculated from the subject's insulin-to-carbohydrate (I:C) ratio to match a 75-gram carbohydrate challenge. Rule 450 will be used for carbohydrate counting and insulin dose calculation in this study (see [Appendix 3](#)).

Prior to dose administration, a peripheral catheter for blood sampling will be placed into a vein ideally located within the antecubital fossa. The hand of the arm used for blood sampling will be kept warm by use of a heated hand box to increase blood flow and achieve “arterialized” samples. The subject will remain supine and kept warm and be allowed to drink only water (ad libitum).

Once the catheter and hand box are in place, study drug(s) will be administered SC over 1 to 3 seconds to the abdomen (around the umbilicus). Co-administered regular insulin plus pramlintide injections should be administered to opposite sides of the abdomen (ie, left and right peri-umbilicus, opposite quadrants). Injection sites should be rotated to avoid injecting at a previously used site.

To monitor for hypoglycemia, BGM will be performed in real time at each subject's bedside at 10, 20, 30, 40, 50, 60, 90, 120, and 180 minutes post dosing at Visit 2 through 4. BGM measurements from the cool hand are allowed.

To evaluate drug PD (plasma glucose response), blood samples are to be drawn at 10 ± 2 minutes before and immediately (-2 to 0 minutes) prior to study drug injection. After study drug injection, blood samples also will be collected at 10, 20, 30, 40, 50, 60, 90, 120, 150, 180, 240, 300, and 360 minutes post-dosing (window allowance of ± 2 minutes). After the 60-minute postdose time point, the subject's hand must be reinserted into the heated box for at least 10 minutes prior to the next blood collection.

To evaluate drug PK (plasma insulin/pramlintide concentrations), blood samples are to be drawn at 10 ± 2 minutes before and immediately (-2 to 0 minutes) prior to study drug injection. After study drug injection, blood samples also will be collected at 10, 20, 30, 40, 50, 60, 90, 120, 150, 180, 240, 300, and 360 minutes post-dosing (window allowance of ± 2 minutes).

Within 2 minutes after the 30 minutes post-dose blood draw, a standardized 75-gram oral glucose challenge should be ingested (within 5 to 10 minutes) by the subject.

After the last blood collection (at 360 minutes post-study drug administration), subjects are to be provided a regular meal and insulin (per investigators' discretion).

At 30, 90, and 360 minutes (± 2 minutes) post-dose, injection sites will be evaluated by the investigator using the modified Draize scale ([Appendix 1](#)). Additionally, subjects will complete an injection site discomfort questionnaire at 10 and 30 minutes (± 2 minutes) post-dose ([Appendix 2](#)).

A subject may be discharged from the clinic, per investigator's criteria, when the following has occurred:

- Subject has consumed their meal
- Subject has returned to their usual medication regimen, including insulin
- Subject's capillary glucose concentration is confirmed to be > 100 mg/dL
- Subject is considered medically stable

Any time during the visit if hypoglycemia occurs (ie, blood glucose < 70 mg/dL), the subject will be rescued with IV dextrose using the following formula to calculate the dose of dextrose:

$$D50\% \text{ mL} = (100 \text{ minus BG}) \times 0.4$$

Where D50% = the dose of IV dextrose, mL = the volume of dextrose, BG = the subject's hypoglycemic blood glucose value ([ADA, 2008; Joslin Center, 2013](#))

The dose of dextrose should be administered slowly, over 2 to 5 minutes.

If D50% is administered, then blood glucose will be remeasured by blood glucose meter at 10, 20, and 30 minutes following the end of administration of IV dextrose.

Successful plasma glucose recovery should be confirmed (ie, glucose returns to ≥ 70 mg/dL) and the subject medically stabilized. When the subject is medically stable, they can be discharged from the clinic (per criteria above).

After a first washout period of 7 to 11 days, subjects will return to the clinic for Treatment Period 2 (Visit 3) and the treatment visit procedures will be repeated with each subject crossed over to the next randomized study drug treatment sequence. Upon check-in and completion of morning activities, the subject will receive their second administration of study drug(s).

After a second washout period of 7 to 11 days, subjects will return to the clinic for Treatment Period 3 (Visit 4) and the treatment visit procedures will be repeated with each subject crossed over to the last randomized study drug treatment sequence. Upon check-in and completion of morning activities, the subject will receive their third administration of study drug(s).

During the Treatment Periods, subjects will undergo vital sign measurements; AE assessments; concomitant medication assessments; and pregnancy testing for females of childbearing potential as outlined in the Schedule of Assessments ([Table 2](#)).

Follow-Up

A Follow-Up Visit will be conducted 7 to 11 days after the subject's last dose of study drug(s). Subjects will return to the clinic and undergo a full PE, vital sign measurements, weight, AE assessments, concomitant medication assessments, sample collection for hematology, chemistry, C-peptide, and pregnancy testing for females of childbearing potential.

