
Prior to study drug administration, a peripheral catheter for blood sampling will be placed into a vein ideally located within the antecubital fossa. The hand of the arm used for blood sampling will be kept warm by use of a heated hand box to increase blood flow and achieve “arterialized” samples. The subject will remain supine and kept warm and be allowed to drink only water (ad libitum).
 
Once the catheter and hand box are in place, study drug(s) will be administered SC over 1 to 3 seconds to the abdomen (around the umbilicus). Co-administered regular insulin plus pramlintide injections should be administered to opposite sides of the abdomen (ie, left and right peri-umbilicus, opposite quadrants). Injection sites should be rotated to avoid injecting at a previously used site.
 
To monitor for hypoglycemia, BGM will be performed in real time at each subject's bedside at 10, 20, 30, 40, 50, 60, 90, 120, and 180 minutes post dosing at Visit 2 through 4.
 
To evaluate drug PD (plasma glucose response) and PK (plasma insulin/pramlintide concentrations), blood samples are to be drawn at the time points described in the Schedule of Assessments (Table 2).
 
Within 2 minutes after the 30 minutes post-dose blood draw, a standardized 75-gram oral glucose challenge should be ingested (within 5 to 10 minutes) by the subject.
 
After the last blood collection (at 360 minutes post-study drug administration), subjects are to be provided a regular meal and insulin (per investigators' discretion).
 
Injection sites will be evaluated by the investigator using the modified Draize scale (Appendix 1) and subjects will complete injection site discomfort questionnaires (Appendix 2).
 
A subject may be discharged from the clinic, per investigator's criteria, when the following has occurred:
 
 • Subject has consumed their meal • Subject has returned to their usual medication regimen, including insulin • Subject's capillary glucose concentration is confirmed to be > 100 mg/dL • Subject is considered medically stable 
Any time during the visit if hypoglycemia occurs (ie, blood glucose < 70 mg/dL), the subject will be rescued with IV dextrose using the following formula to calculate the dose of dextrose:
 $\text{D50\% mL} = (100 \text{ minus BG}) \times 0.4$ 
Where D50% = the dose of IV dextrose, mL = the volume of dextrose, BG = the subject's hypoglycemic blood glucose value
 
The dose of dextrose should be administered slowly, over 2 to 5 minutes.
 
If D50% is administered, then blood glucose will be remeasured by blood glucose meter at 10, 20, and 30 minutes following the end of administration of IV dextrose. Successful plasma glucose recovery should be confirmed (ie, glucose returns to ≥ 70 mg/dL) and the subject medically stabilized. When the subject is medically stable, they can be discharged from the clinic (per criteria above).
 
After a first washout period of 7 to 11 days, subjects will return to the clinic for Treatment Period 2 (Visit 3) and the treatment visit procedures will be repeated

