9.1.1. PRAM9

PRAM9 is a stable, liquid, and ready-to-use co-formulation of pramlintide and regular insulin for SC injection.

The pramlintide and insulin injection drug product is prepared as a sterile liquid for injection that is packaged as a 0.9 mg/mL pramlintide + 3.5 mg/mL insulin solution for injection in a 3-mL glass vial (2.5 mL fill volume).

The dose of PRAM9 is to be based upon the subject's historical mealtime insulin dose (based upon the subject's historical carbohydrate: insulin ratio). The historical insulin dose will be reduced by 50% to derive the new insulin dose. The associated pramlintide dose will be related to the dosage of insulin (eg, 9 µg pramlintide per 1 U of insulin).

PRAM9 is to be administered SC (in the abdomen, peri-umbilicus).

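### Scheduled bedside glucose checks for hypoglycemia stop at 180 minutes, although the rescue rule runs all visit and no meal is given until after the 360-minute draw

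*Protocol*

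**What the plan says.** Section 6.1 sets the real-time meter schedule, whose stated purpose is to monitor for hypoglycemia, at each subject's "bedside at 10, 20, 30, 40, 50, 60, 90, 120, and 180 minutes post dosing at Visit 2 through 4". The same times appear in the Synopsis under Methodology ("bedside at 10, 20, 30, 40, 50, 60, 90, 120, and 180 minutes post dosing"), in the Synopsis under Safety assessments, and in footnote 5 of Table 2.

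The rescue rule in Section 6.1 has no end time: "Any time during the visit if hypoglycemia occurs", defined as blood glucose below 70 mg/dL, IV dextrose is given. The volume in mL is (100 - BG) x 0.4.

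On intake, Section 6.1 allows only water during the procedure, apart from the challenge straight after the 30-minute draw, when "a standardized 75-gram oral glucose challenge should be ingested (within 5 to 10 minutes) by the subject". Food comes later: "After the last blood collection (at 360 minutes post-study drug administration), subjects are to be provided a regular meal and insulin", with the insulin at the investigator's discretion.

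Venous samples for plasma glucose continue at 240, 300 and 360 minutes. Section 11.1 leaves their handling to a laboratory manual.

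**The concern.** The rescue rule cannot operate without a glucose value, and the schedule that supplies one in real time ends halfway through the observation period. From 180 to 360 minutes a subject with type 1 diabetes has study insulin on board, basal insulin from the evening before, and nothing but water by mouth. A symptomatic low would probably prompt a check. An asymptomatic one might be found only when the plasma samples are analysed, after the time for rescue has passed.

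The protocol itself treats lows in this window as relevant. Section 12.1.1 makes hypoglycemia an adverse event of special interest, Section 8.5 requires every occurrence to be recorded, and Section 13.3.2 defines endpoints below 70 and 54 mg/dL over 0-360 minutes. The 360-minute point also comes just before any meal insulin, and no reading is required immediately before that insulin.

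**Working it through.** The protocol gives no figure to reproduce here, so the check compares schedules and counts readings.

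**Meter schedule against venous draws**

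| Window after dosing | Venous glucose draws (min) | Scheduled meter readings (min) |
|---|---|---|
| 0 to 180 min | 10, 20, 30, 40, 50, 60, 90, 120, 150, 180 | all of these except 150 (9 readings) |
| After 180 to 360 min | 240, 300, 360 | none |

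**Coverage**
- Share of the observation period with no scheduled meter reading: (360 - 180) / 360 = 50%.
- Longest interval up to 180 minutes: 180 - 120 = 60 minutes.
- Interval after the last reading, to the end of observation: 360 - 180 = 180 minutes.
- With readings at 240, 300 and 360 added, the longest interval is the maximum of 180 - 120, 240 - 180, 300 - 240 and 360 - 300, which is 60 minutes. That equals the longest interval the protocol already accepts.

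**Other text that might fill the gap**
- Section 10.2.2 names a pre-dose meter reading and a discharge condition of capillary glucose above 100 mg/dL. The discharge reading has no clock time and is listed alongside the meal.
- Sections 6.1 and 8.5 require meter readings at 10, 20 and 30 minutes after dextrose, but only once a low has been found and treated.
- Section 12.13 keeps an investigator on site for 6 hours after dosing and allows safety measurements to be repeated under SOPs or at a physician's request. It sets no timed glucose reading.

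None of these schedules a reading between 180 and 360 minutes.

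**Cost of adding three readings**
- Subject-periods: 18 x 3 = 54.
- Extra readings: 54 x 3 = 162, on top of 54 x 9 = 486 already planned. Subjects replaced under Section 8.4 were never dosed, so they add none.
- Dextrose per additional rescue: (100 - 69) x 0.4 = 12.4 mL at 69 mg/dL, and (100 - 54) x 0.4 = 18.4 mL at 54 mg/dL, with 3 follow-up meter readings each time.
- Glucose endpoints in Section 13.3.2 explicitly defined on 0-360 minutes: 4 proportional times, 2 AUCs and 2 AOCs, 8 in all. Four of them concern values below 70 or 54 mg/dL.

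**The case against.** The strongest reply is that nothing here is an error. The four statements of the schedule agree, and a rescue rule valid all visit does not contradict a finite minimum set of readings. Staff see the subject at all three late draws, repeat heart rate and blood pressure and inspect the injection site at 360 minutes, and an investigator is present for 6 hours. Section 12.13 also provides expressly for repeat measurements. The laboratory manual, which is not available here, may say that late samples are read promptly.

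The risk is also limited. The insulin dose is matched to the 75 g challenge and is halved for PRAM9 ("The historical insulin dose will be reduced by 50% to derive the new insulin dose") and for the co-administered treatment (Section 9.1.3), so only the regular-insulin period carries the full dose. The meal insulin is discretionary and comes with food. The 50% figure describes a schedule and is not a measure of risk.

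Most of this stands, and it is why the point is optional. It does not supply a timed reading in the second half of the period, and checks prompted by symptoms can miss asymptomatic lows.

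The change also has a cost to the data. More detection means more dextrose, which shortens time below 70 and 54 mg/dL. If lows cluster in the full-dose regular-insulin period, that effect could differ between treatments. This should be disclosed, but it is no reason to leave lows undetected, because the existing rule already calls for those rescues.

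**Conclusion.** The point holds as a modest, optional safety improvement. As written, the protocol schedules no real-time glucose reading for 180 of the 360 minutes observed, while its rescue rule depends on one. The weakness is in scheduled detection; the ability to treat is intact. No bias between treatments under the current plan is claimed, and the 0-180 minute primary endpoint is not affected.

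The conclusion assumes that the late venous samples are not read in real time. The protocol is silent on this, and if the laboratory manual requires immediate reading, a clarifying sentence is enough. The protocol gives no hypoglycemia rate for this window, so the number of lows that might be missed cannot be estimated.

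**What to change.** Add bedside meter readings at the existing 240, 300 and 360 minute draws, and take the 360-minute reading before the meal and insulin. Amend Section 6.1, footnote 5 of Table 2, and the Synopsis statements under Methodology and Safety assessments. Alternatively, state that the glucose samples at those times are read immediately and trigger the rescue rule.

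The cost is at most 162 extra readings in subjects already being bled at those times. Section 6.1 says "BGM measurements from the cool hand are allowed", so the heated sampling hand need not be disturbed. The four wording changes need IRB/IEC approval before use (Section 17.1) and could travel with another amendment. Dextrose given between 180 and 360 minutes should be recorded with its time and treatment period, so that its effect on the 0-360 minute secondary endpoints can be seen.
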